1.7 Research Hypotheses

1.7.1 Primary Hypothesis

The administration of MEDI0382 SC once daily will improve glycemic control in overweight/obese subjects with T2DM treated concurrently with dapagliflozin and metformin.

1.7.2 Secondary Hypotheses

- The administration of MEDI0382 SC will have an acceptable safety profile and be well tolerated when coadministered with dapagliflozin and metformin.
- The PK profile of MEDI0382 will remain unchanged in the presence of coadministered dapagliflozin and metformin.
- The immunogenicity profile of MEDI0382 will remain unchanged in the presence of coadministered dapagliflozin and metformin.
- The administration of MEDI0382 decreases 24-hour glycemic variation when coadministered with dapagliflozin and metformin.

2 OBJECTIVES AND ENDPOINTS

2.1 Primary Objective and Associated Endpoints

Table 2.1-1 Primary Objective(s) and Associated Endpoints

Type	Objective	Endpoints
Efficacy	To compare the change in glucose AUC as measured by a standardized MMTT in subjects treated with dapagliflozin and metformin receiving MEDI0382 or placebo for 28 days	
 • Change from baseline (Day-1) to the end of 28 days of treatment (Day 28) in glucose AUC_{0-4h} as measured by a MMTT • Percentage change from baseline (Day -1) to the end of 28 days of treatment (Day 28) in glucose AUC_{0-4h} as measured by a MMTT

AUC = area under the concentration-time curve; AUC_{0-4h} = area under the concentration-time curve from zero to 4 hours; MMTT = mixed meal tolerance test;

2.2 Secondary Objectives and Associated Endpoints

Table 2.2-1 Secondary Objectives and Associated Endpoints

Type	Objective ^a	Endpoints
Safety	To compare the safety and tolerability profile of MEDI0382 (titrated up to a dose level of 300 µg SC) compared to placebo after 28 days of treatment in subjects treated with dapagliflozin and metformin	Measures of safety and tolerability include: 
 • Incidence of TEAEs and TESAEs • Clinically important changes in 12-lead ECG, vital signs (including 24-hour HR and BP), physical examination, and clinical laboratory evaluations
PK	To evaluate the PK profile of MEDI0382 and dapagliflozin (in subjects treated with dapagliflozin, metformin, and MEDI0382) and dapagliflozin (in subjects treated with dapagliflozin, metformin, and placebo)	PK profile of both MEDI0382 and dapagliflozin administered simultaneously and dapagliflozin administered with placebo include: 
 • AUC_{0-inf}, AUC_{0-last}, and AUC_{tau} • C_{max}, t_{max}, t_{1/2}, and CI/F
Immunogenicity	To evaluate the immunogenicity profile of MEDI0382 (titrated up to a dose level of 300 µg) in subjects treated with dapagliflozin and metformin receiving placebo or MEDI0382 for 28 days	
 • Immunogenicity as measured by the presence of ADA to MEDI0382 (and titer if positive) during dosing and follow-up periods
Efficacy/PD	To evaluate 24-hour glucose control as measured by CGM in subjects treated with dapagliflozin and metformin receiving MEDI0382 or placebo for 28 days	
 • Change from baseline to the end of dosing at each dose level (Days 7, 14, and 28) in glucose AUC_{24h} as measured by CGM • Change from baseline to the end of dosing at each dose level (Days 7, 14, and 28) in 24-hour mean glucose as measured by CGM • Change from baseline to the end of dosing at each dose level (Days 7, 14, and 28) in SD of 24-hour glucose readings as measured by CGM • Change from baseline to Days 7, 14, and 28 in the CV (ratio of SD:mean over 24 hours) of glucose readings as measured by CGM • Change from baseline to Days 7, 14, and 28 in the MAGE of 24-hour glucose readings as measured by CGM • Change from baseline to Days 7, 14, and 28 in the percentage of 24-hour glucose readings obtained from CGM that fall within the euglycemic range of ≥ 70 mg/dL (≥ 3.9 mmol/L) and ≤ 180 mg/dL (≤ 10.0 mmol/L) • Change from baseline to Days 7, 14, and 28 in the percentage of 24-hour glucose readings obtained from CGM that fall within hyperglycemic (high

Table 2.2-1 Secondary Objectives and Associated Endpoints

Type	Objective ^a	Endpoints
		glucose) range of > 180 mg/dL (> 10.0 mmol/L) 
 • Change from baseline to Days 7, 14, and 28 in the percentage of 24-hour glucose readings obtained from CGM that fall within the hypoglycemic range of < 70 mg/dL (< 3.9 mmol/L) • Change from baseline to Days 7, 14, and 28 in the percentage of 24-hour glucose readings obtained from CGM that fall within the clinically significant hypoglycemic range of < 54 mg/dL (3.0 mmol/L)

AUC_{24h} = area under the concentration-time curve at 24 hours; AUC_{0-inf} = area under the concentration-time curve from zero to infinity; AUC_{0-last} = area under the concentration-time curve from zero to last observation; AUC_{tau} = area under the concentration-time curve during the dosing period; BP = blood pressure; Cl/F = apparent clearance; CGM = continuous glucose monitoring; C_{max} = maximum-observed serum drug concentration; CV = coefficient of variation; ECG = electrocardiogram; HR = heart rate; MAGE = mean amplitude of glucose excursion; PD = pharmacodynamics; PK = pharmacokinetics; SC = subcutaneous; SD = standard deviation; t_{1/2} = terminal elimination half-life; TEAEs = treatment-emergent adverse events; TESAEs = treatment-emergent serious adverse events; t_{max} = time to maximum-observed serum drug concentration

^a Secondary efficacy, safety, PK, immunogenicity, and PD endpoints will be evaluated in subjects receiving MEDI0382 or placebo coadministered with 10 mg dapagliflozin and metformin.

2.3 Exploratory Objectives and Associated Endpoints

Table 2.3-1 Exploratory Objectives and Associated Endpoints

Type	Objective ^a	Endpoint
Efficacy	To compare additional measures of glucose control (FPG, HbA1c) in subjects treated with dapagliflozin and metformin receiving MEDI0382 or placebo for 28 days	
 • Change from baseline (Day -1) to Day 28 in FPG • Change from baseline (Day -2) to Day 28 in HbA1c
PD	To evaluate pancreatic and incretin hormone AUC profiles (ie, active GLP-1, glucagon, insulin, and c-peptide) as measured by MMTT in subjects treated with dapagliflozin and metformin receiving MEDI0382 or placebo for 28 days	
 • Change from baseline (Day -1) to Day 28 in GLP-1, glucagon, insulin, and c-peptide AUC_{0-4h} as measured by MMTT
PD	To compare the fasting FFA levels in subjects treated with dapagliflozin and metformin receiving MEDI0382 or placebo for 28 days	
 • Change from baseline (Day -1) to Days 7, 14, and 28 in fasting FFA level
PD	To compare plasma ketone profile (β-hydroxybutyrate) in subjects treated with dapagliflozin and metformin receiving MEDI0382 or placebo for 28 days	
 • β-hydroxybutyrate profile to include AUC_{0-inf}, AUC_{0-last}, C_{max}, and t_{max}

Table 2.3-1 Exploratory Objectives and Associated Endpoints

Type	Objective ^a	Endpoint
Efficacy	To compare the change in body weight after 28 days of treatment with MEDI0382 or placebo in subjects treated with dapagliflozin and metformin	
 Change from baseline (Day 1) to Day 29 in body weight (kg) Percentage change from baseline (Day 1) to Day 29 in body weight (kg) Proportion of subjects achieving $\geq 5\%$ body weight loss from baseline (Day 1) to Day 29
PD	To evaluate 24-hour urinary glucose excretion in subjects treated with dapagliflozin and metformin receiving MEDI0382 or placebo	
 Total glucose excreted in urine collected for 24 hours

AUC = area under the concentration-time curve; AUC_{0-4h} = area under the concentration-time curve from zero to 4 hours; AUC_{0-inf} = area under the concentration-time curve from zero to infinity; AUC_{0-last} = area under the concentration-time curve from zero to last observation; C_{max} = maximum-observed serum drug concentration; FFA = free fatty acid; FPG = fasting plasma glucose; GLP-1 = glucagon-like peptide-1; HbA1c = hemoglobin A1c; MMTT = mixed meal tolerance test; PD = pharmacodynamics; t_{max} = time to maximum-observed serum drug concentration

^a Exploratory endpoints will be evaluated after 28 days of treatment in subjects receiving MEDI0382 or placebo alongside 10 mg dapagliflozin and metformin administered simultaneously as background therapy.

3 STUDY DESIGN

3.1 Description of the Study

3.1.1 Overview

This is an exploratory randomized, double-blind, placebo-controlled study to evaluate the efficacy and safety of MEDI0382 versus placebo in overweight/obese subjects with T2DM treated with dapagliflozin and metformin dual therapy.

The study will enroll subjects with T2DM treated either with metformin monotherapy or with metformin and dapagliflozin dual therapy. After the screening period of up to 60 days, subjects treated with metformin monotherapy only will enter a 4-week run-in period where subjects will be administered oral dapagliflozin 10 mg a day, which will be provided by the sponsor. Enrolled subjects that are already treated with metformin and dapagliflozin dual therapy will continue this dual therapy throughout the study and can be randomized after the screening period without entering the run-in period. All subjects (ie, on monotherapy and dual therapy) entering the double-blind treatment period will receive dapagliflozin 10 mg a day, which will be provided by the sponsor.

Forty-six subjects are expected to participate in the study for up to 20 weeks including a screening period of up to 60 days, a 4-week run-in period (for subjects on metformin

monotherapy only), a 4-week treatment period, and a 4-week follow-up posttreatment period. There will be a total of 2 inpatient stays with a duration of 2 to 3 days.

Four-week run-in period

After screening, subjects on metformin monotherapy only will begin an open-label, run-in period on Day -28 and will receive oral dapagliflozin 10 mg a day for 28 days prior to randomization. On Day -14, subjects will return to the clinical unit for an abbreviated physical examination, vital signs, and blood collection for safety laboratory assessments.

Subjects on dual therapy (metformin plus dapagliflozin) can be randomized after the screening period. In addition, all subjects will be given diet and lifestyle advice to follow for the duration of the study.

Four-week treatment period

On Day -2, subjects will be admitted to the clinical unit for 1 to 2 nights (ie, subject may choose to stay a second night or leave the clinic). Subjects will undergo initial safety assessments including but not limited to an abbreviated physical examination, medical history, vital signs, blood collection for laboratory tests (eg, lactate, pH, and HbA1c), urine tests (eg, pregnancy, drug and alcohol screen), and training in SC injection administration. An ABPM device will be fitted on Day -2 and worn for 24 hours. On Day -1, after an overnight fast of approximately 10 hours, subjects will undergo a mixed-meal tolerance test (MMTT). Subjects will be asked to drink 1 entire can of Ensure Plus[®] (a nutritional supplement containing the components of fat, carbohydrate, and protein that make up a standard MMTT) within 5 minutes. Blood samples will be drawn after consumption of the drink for quantification of glucose, active GLP-1, insulin, c-peptide, and glucagon per the treatment schedule ([Table 4.2.3-1](#)). At this visit, eligibility criteria verification and additional training in SC injection administration will be performed. Blood will be collected for laboratory tests (eg, FFA, FPG), dapagliflozin PK, and ketone PK sampling. After the MMTT on Day -1, the subject will be fitted with a continuous glucose monitoring (CGM) device on the contralateral arm to the ABPM, which will expire and be replaced every 14 days. Subjects will be expected to wear the CGM sensor continuously for the duration of treatment ([Section 4.2.3](#) and [Table 4.2.3-1](#) for additional details). Subjects will also be expected to conduct daily finger-prick testing for ketone measurements throughout the treatment period.

Following completion of the MMTT test and assessments on Day -1, subjects are given the option to remain in the unit or return home, but subjects must ensure they undergo an

overnight fast for approximately 10 hours. Discharged subjects will return to the clinic on Day 1. Subjects can be randomized after confirming eligibility at any time from Day -1 to Day 1 (predose) to receive either MEDI0382 or placebo. On Day 1, following the overnight fast, dosing of MEDI0382 SC or placebo SC will commence after predose safety measures including but not limited to vital signs, an ECG, and blood collection for laboratory tests (eg, lactate, pH); [REDACTED] dapagliflozin and ketones PK sampling; and measurement of weight are performed. A 24-hour urinary collection for glucose excretion will be collected from Day 1 to Day 2. Subjects will be monitored for safety, glucose, and ketones, and will be discharged from the unit approximately 6 hours postdose. Capillary glucose and ketones monitoring will be done at the site using a glucometer. The subject will return to the unit on Day 2 for safety monitoring and supervision of investigational product administration. The subjects will be discharged with the same syringe pack of investigational product supplies and will continue to self-administer investigational product on an outpatient basis.

[figure not shown]
Subjects will then return to the clinical unit at weekly intervals until a maintenance dose of 300 µg is achieved. Subjects will return to the unit for outpatient visits on Days 7, 8, 14, 15, and 22 to undergo safety assessments including but not limited to an abbreviated physical examination and ECG (Days 7, 14, and 22), vital signs (all visits with ABPM fitted on Day 14 only), urine tests (eg, pregnancy test on Day 14 and Day 22), and blood collection for laboratory tests (Days 7, 14, and 22). MEDI0382, dapagliflozin, and ketones PK sampling will be performed on Days 7, 8, 14, and 15. Uptitration of SC investigational product will occur on Day 8 and Day 15. After uptitration of investigational product, subjects will be monitored for safety, capillary glucose and ketones and will be discharged 6 hours postdose. A 10-hour overnight fast is required prior to visits on Days 7 and 14, and a standardized breakfast meal will be provided 2 hours postdosing on these days. The CGM device will be replaced on Day 14.

Subjects will return to the unit for admission on Days 27 to 29 (Visit 11) to undergo final safety assessments including but not limited to an abbreviated physical examination, an ECG, and urine tests (eg, pregnancy and drug and alcohol screening) on Day 27 and vital signs (including ABPM) and blood collection for laboratory tests (eg, lactate, pH, HbA1c) on Day 28. On Day 28, following an overnight fast of 10 hours, a final MMTT will be performed. On Day 28, PK sampling of MEDI0382, dapagliflozin, and ketones will be taken relative to time zero of administration of investigational product. A 24-hour urine collection for glucose secretion will also be performed from Day 28 to Day 29. On Day 29, vital signs, a measurement of weight, and [REDACTED] MEDI0382, dapagliflozin, and ketones PK will be performed. Subjects will be discharged if no safety

concerns are identified. Subjects will then enter the 4-week, posttreatment safety follow-up period, and they will continue to wear the CGM until approximately 28 days after the last dose of investigational product.

Throughout the entire combination treatment period and in the follow-up period, subjects will be required to continue wearing the CGM sensor (up to 28 ± 4 days after the last dose of investigational product) and to test their ketone level once daily prebreakfast (up to 14 ± 2 days after the last dose) using the testing strips provided.

Figure 3.1.1-1 Study Flow Diagram

BMI = body mass index; HbA1c = hemoglobin A1c; MTD = maximum-tolerated dose; N = number of subjects; QD = once daily; SC = subcutaneous; T2DM = type 2 diabetes mellitus.

* Run-in period only for subjects on metformin monotherapy only at screening

** Subject on metformin and dapagliflozin dual therapy at screening move directly from screening to double blind treatment period

The endpoints to be measured in this study are described in Section 2.

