Subjects will be admitted to the clinical unit on Day -2. Study subjects will undergo initial safety assessments including but not limited to blood collection for laboratory tests, medical history, abbreviated physical examination, vital signs, and training on SC injection administration. At this time, an ambulatory blood pressure monitoring (ABPM) device will be fitted on Day -2 and worn for 24 hours. Subjects will be expected to conduct daily finger-prick testing for ketone measurements throughout the treatment period. On Day -1, after an overnight fast of approximately 10 hours and verification of eligibility criteria, subjects will undergo their first MMTT. After the MMTT, subjects will be fitted with a CGM sensor on the contralateral arm to the ABPM, which will expire and be replaced every 14 days. Subjects will be expected to wear this sensor for the duration of treatment. Other procedures on Day -1 include blood collection for laboratory tests, dapagliflozin and ketones PK sampling, and training on SC administration. On Day -1, the subject will have the option to remain in the unit or return home. Discharged subjects must ensure they undergo an overnight fast for approximately 10 hours, and they will return the clinic on Day 1. Subjects can be randomized after confirming eligibility at any time from Day -1 to Day 1 (predose) to receive either MEDI0382 or placebo. On Day 1, following an overnight fast, dosing will commence after predose safety measures including vital signs, an ECG, and blood collection for laboratory tests; blood collection for dapagliflozin PK, ketones PK, and ADA; and measurement of weight are performed. Subjects will then receive the following:

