3.1.2 Treatment Regimen

Four-week run-in period

Following screening, subjects previously treated with metformin monotherapy only will enter an open-label, run-in period and will receive oral dapagliflozin 10 mg a day for 4 weeks, which will be provided by the sponsor.

Four-week treatment period

Following the run-in period for subjects on metformin monotherapy or the screening period for subjects on metformin and dapagliflozin dual therapy, subjects will be randomized as follows:

- MEDI0382 SC once daily (titrated up from 100 µg for 7 days to 200 µg for 7 days and to 300 µg for 14 days) in the morning for 28 days (N = 23) or
- Placebo SC once daily in the morning for 28 days (N = 23)

The sponsor will provide dapagliflozin to all subjects entering the treatment period.

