- ^b On Day -1, following completion of the MMTT test, subjects are given the option to remain in the unit or return home. Discharged subjects must ensure they undergo an overnight fast for approximately 10 hours, and they will return to the clinic on Day 1.

- ^c Body weight should be measured in the morning prior to breakfast on Day 1 (predose on Day 1) and on Day 29. The subject should take off their shoes and remove bulky clothing. Calibrated scales should be used.
- ^d A single, digital ECG recording should be performed predose after the subject has rested for 10 minutes on Day 1, 7, 14, 22, and 27.
- ^e **Vital Signs schedule:** Vital signs include BP, HR, RR, and body temperature. On days when ABPM device is due to be checked, a predose set of vital signs should be performed only prior to application of the ABPM cuff. BP should be measured once at heart level in the nondominant arm where possible, and opposite to the arm where the CGM device is applied. The subject should seat and rest for 10 minutes prior to the measurement. Both lying and standing measurements should be taken.
- Day -2, 14, and 28: vital signs to be taken prior to fitting ABPM
 - Day 1: vital signs to be taken predose (-15 minutes); immediately after dosing (+ 3 minutes); 15, 30, and 60 minutes (\pm 5 minutes) postdose; and 2 hours (\pm 10 minutes) postdose
 - Day 15 and 29: vital signs to be taken once ABPM is removed
 - Day 7, 8, and 22: vital signs to be taken at no specific time point
- ^f Subjects will be fitted with the ABPM device shortly after they arrive at the clinical unit. Subjects may be involved in practice inflations. On Day -2, 14, and 28, ABPM should be applied predose. From Day 14 to Day 15, the subject will wear the monitor/cuff for approximately 24 hours (including overnight) and will remove the device at home at the end of the 24-hour period. Subjects will return the device to the clinic. On Day -1 and Day 29, the device will be removed at the clinic during the inpatient stay.
- ^g Randomization may occur any time from Day -1 to Day 1 (predose).
- ^h Normal saline will be used for SC injection administration training.
- ⁱ Metformin and dapagliflozin to be administered before investigational product administration. For PK sample collection, dapagliflozin should be administered by staff at the clinic on Days -1, 1, 7, 8, 14, 15, and 28 shortly before investigational product.

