- ^q **MMTT schedule:** The MMTT is conducted on Day -1 and Day 28 following a minimum 10-hour fast the day before. On Day -1, the MMTT starts 2 hours after dapagliflozin administration. On Day 28, the MMTT starts 2 hours after investigational product (MEDI0382 or placebo) and dapagliflozin administration. A blood sample for glucose metabolism panel (glucose, insulin, c-peptide, glucagon, and active GLP-1) will be taken immediately prior to the subject drinking one entire can of Ensure Plus as a standardized meal (ie, “0 minutes”). In addition, blood samples for glucose metabolism panel will be drawn at 15, 30, 45, 60, 90, 120, 180, and 240 minutes (\pm 5 minutes) after consumption of the standardized meal. Additional sampling for glucagon, insulin, c-peptide, and glucose to be taken at 6, 8, 12, and 24 hour after time 0 (\pm 30 minutes) of the standardized meal administration on Days -1 and Day 28.
- ^r **Standardized breakfast meal:** On Day 7 and 14, a standardized breakfast meal will be provided approximately 2 hours after dapagliflozin and investigational product administration. The meal will have approximately 450 kilocalories and will consist of 1 egg, 2 slices of white bread, 1 slice of Swiss cheese and 1 cup (240 ml) of orange juice (approximately 30% fat, 15% protein and 55% carbohydrates).
- ^s Twenty-four-hour urinary collection for measurements of glucose excretion to start first thing in the morning soon after waking on Day 1 and Day 28. Instruct the subject to pass urine soon after waking and flush down the toilet. Note the exact time this was done. The collection of urine will start from this time. Proceed to collect every drop of urine day and night for 24 hours and finish by passing urine the next morning at exactly the same time collection was started the day before. This urine should also be added to the bottle.
- ^t Breath alcohol testing is acceptable as an alternative to urine testing.
- ^u Subjects will be provided with a ketones monitor and strips for capillary blood ketone testing and will be instructed to test once a day (prebreakfast) and to do additional tests including glucose if they feel unwell. Subjects will be asked to record ketone values in a paper diary, which will be provided and checked by study staff.

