- ^v CGM device to be fitted and worn continuously throughout the study. The sensor should be applied to the arm, taking into account which side the subject sleeps on and also which side the ABPM device will be applied. The sensor applied to the skin is single use and may not be reattached once removed.

- ^w CGM sensors last 14 days and should be changed at 14-day intervals at the same time of day (± 20 minutes) as originally applied on Day -1. For example, if the sensor is applied at 6:00 am on Day -1, it should also be applied at 6:00 am (± 20 minutes) predose on Day 14 and 28. If the sensor fails, or needs to be replaced, it should be reapplied as soon as possible.

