4.3.6 Pharmacodynamic Evaluation and Methods

4.3.6.1 Training for Application and Wearing of Continuous Glucose Monitoring Sensor

A Freestyle Libre[®] Pro CGM device will be used to measure interstitial glucose levels during the study. The Freestyle Libre[®] Pro CGM device measures interstitial glucose levels every 15 minutes continuously for 2 weeks and does not require any calibration or periodic near-field/bluetooth connections with the device to perform this function. The Freestyle Libre[®] Pro CGM device does not permit flash glucose measurements. Study-site staff and investigators should avoid periodic reviews of interstitial glucose levels during the study to avoid the risk of unblinding. However, should a subject experience an AE or SAE, and the investigator deems information acquired by CGM to be useful in the subject's ongoing management, interstitial glucose readings may be reviewed by the investigator as described in the manual, but they should avoid review of baseline readings taken on Day -1. The CGM sensor, which is a small plastic circular device of 35 mm diameter and 5 mm depth, should be applied to the arm, taking into account which side the subject sleeps on and also which side the ABPM device will be applied. The selected site should be shaved where necessary, and a sterile alcohol wipe (supplied with the kit) should be used to clean the site prior to application. Study-site staff should refer to the training materials and manual for application of the CGM sensor. Subjects will be expected to wear the CGM sensor continuously up until the time of a sensor change, which should occur within 14 days. Moreover, subjects are to be advised that they may bathe, shower, or swim (up to 3 m depth for up to 30 minutes) while wearing the CGM sensor. The CGM sensor should be removed at the specified times in the schedule of assessments (CGM sensor change). At this time, the site should be inspected and cleaned, and a new CGM sensor may be reapplied. Ideally, the new sensor should be applied close to the original site but taking into account the subject's preference on site. The CGM sensor should be changed at the same time of day (\pm 20 minutes) as originally applied on Day -1. CGM sensors are single use and cannot be reapplied once removed. CGM sensors may only be applied to the upper arm and not to any other site in the body. It should be noted that monitors should remain at the study site and not be provided to subjects to take home.

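### The protocol gives two conflicting times for fitting the first CGM sensor; if it goes on after the Day -1 meal test, the nine 24-hour CGM endpoints have roughly 16 to 22 h of pre-dose baseline, not 24 h

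*Protocol*

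**What the plan says.** **Time of first fitting.** Two places put it after the Day -1 MMTT. Protocol 3.1.1 has "After the MMTT on Day -1, the subject will be fitted with a continuous glucose monitoring (CGM) device", and the synopsis (four-week treatment period) has "After the MMTT, subjects will be fitted with a CGM sensor on the contralateral arm to the ABPM". No earlier CGM is scheduled.

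**Timing around it.** Footnote q to Table 4.2.3-1 states "On Day -1, the MMTT starts 2 hours after dapagliflozin administration" and runs the meal-test panel to 240 minutes. Footnote i states "dapagliflozin should be administered by staff at the clinic on Days -1, 1, 7, 8, 14, 15, and 28 shortly before investigational product". Protocol 3.1.2 has SC dosing in the morning. No clock times are fixed.

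**Sensor changes.** Footnote w and Protocol 4.3.6.1 require changes at the clock time of the Day -1 application, within 20 minutes. Footnote w then illustrates: "For example, if the sensor is applied at 6:00 am on Day -1, it should also be applied at 6:00 am". It continues that this is predose on Days 14 and 28.

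**Baseline.** SAP 3.4.2.1 lists nine CGM endpoints, all changes from baseline in 24-hour quantities at Days 7, 14 and 28. The general rule (Protocol 4.8.1, SAP 3.1) takes the last valid assessment before first administration. The only CGM-specific wording is in Protocol 4.3.6.1, where investigators who look at readings for a safety reason are told that "they should avoid review of baseline readings taken on Day -1". That names a day and no hours. The SAP leaves specifications, and AUC calculation when values are missing, to the SPP (SAP 1 and 3.4.2.2).

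**The concern.** A change from baseline in a 24-hour quantity needs a baseline that covers the same 24 hours as the later days. A sensor fitted after the meal test has not been in place for a day when the first SC dose is given, and readings after that dose cannot count as baseline.

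The gap is systematic. It falls in the hours after the morning dose and always takes in at least the end of the meal test. Days 7 and 14 have a standardized breakfast 2 h postdose, and Day 28 has the second MMTT. The later days therefore contain a standardized post-dose meal that the baseline omits. SD, CV and MAGE, which bear on the secondary hypothesis of reduced 24-hour glycemic variation (Protocol 1.7.2), would be measured at baseline without that excursion.

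The protocol also gives sites two incompatible instructions, so different sites could collect baselines of different length.

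**Working it through.** The documents give no figure for CGM baseline hours, so there is none to reproduce. What follows is time arithmetic.

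**Inputs.** T = time of the Day -1 dapagliflozin dose. The meal test starts at T + 2 h and its panel lasts 4 h (footnote q). The sensor reads every 15 minutes (Protocol 4.3.6.1): 4 per hour, 96 per 24 h. On Day 1, dapagliflozin comes shortly before the SC dose (footnote i), so the first SC dose is taken as T + 24 h + s, where s is the clock shift between the two days. The documents do not fix s.

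**Hours before the first SC dose, following Protocol 3.1.1 and the synopsis.** Fitting = T + 2 + 4 = T + 6 h. Pre-dose hours = 24 + s - 6 = 18 + s. Readings = 4 × (18 + s).

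| Day 1 shift s (assumed) | Pre-dose hours | Readings of 96 |
|---|---|---|
| -2 h | 16 | 64 |
| 0 | 18 | 72 |
| +2 h | 20 | 80 |
| +4 h | 22 | 88 |
| +6 h | 24 | 96 |

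A full day needs s of at least +6 h, for example dapagliflozin at 6:00 am on Day -1 and the SC dose at noon on Day 1. That is hard to square with morning dosing.

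**Other readings of the text, at s = 0.**
- With the lead time of about 2.5 h in Protocol 4.5.1.3: 24 - 6.5 = 17.5 h, 70 readings.
- If fitting waits for the 6 h post-meal sample in footnote q: T + 8 h, so 16 h, 64 readings.
- If baseline means calendar Day -1 only, with dapagliflozin between 6:00 and 10:00 am (assumed): midnight minus (T + 6 h) = 12 to 8 h, 48 to 32 readings.

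**Which hours are missing.** The 24 h before the first SC dose start at T + s. Recording starts at T + 6 h. The gap is T + s to T + 6 h, which always ends with the end of the meal test. At s = 0 it is the whole 6 h after the Day -1 dapagliflozin dose.

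**The contradiction.** A 6:00 am fitting that also followed the meal test would put dapagliflozin at 6:00 am - 6 h = midnight, so the footnote w example describes a fitting before the test. Conversely, a fitting at T + 6 h, carried to Days 14 and 28 by the same-time rule, falls about 6 h after a dose given at clock time T, which is not predose. Under the footnote w example, with a Day 1 dose between 6:00 am and noon (assumed), 24 to 30 h precede the first dose and the baseline is complete.

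**Size for an unscaled AUC.** At equal mean glucose, 18 h gives 1 - 18/24 = 25% less area than 24 h. At a constant 160 mg/dL (assumed): 24 × 160 - 18 × 160 = 3840 - 2880 = 960 hr·mg/dL of apparent change with no true change. The lost meal excursion in SD, CV and MAGE cannot be sized from the documents.

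**The case against.** **The post-meal-test timing is not settled.** Protocol 3.1.1 sends the reader to Table 4.2.3-1 for detail, and footnote w there implies an early fitting and a full baseline. This stands, and it makes the point a contradiction to reconcile. The rule that assessments follow table order does not decide it: the meal-test row precedes the sensor row, but the same table also lists SC dosing above predose blood samples.

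**Day 1 dosing may run late.** Subjects who went home must travel in, and vital signs, ECG, bloods and weight come before the dose. Footnote q also schedules a sample 24 h after the Day -1 meal, at T + 26 h. If that is meant to be predose (not stated), s is at least +2 h and at least 20 h are recorded. This is fair, and is why the size is a range, but no plausible morning shift reaches 24 h.

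**The SPP may define the window.** It may. It cannot recover readings from before the sensor was fitted.

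**Stronger readings the documents do not support.** A reader might infer that the treatment comparison is biased. Both arms follow the same schedule, so it is not, by this alone. A reader might carry the 25% AUC deficit into the treatment effect. In the planned ANCOVA (SAP 3.4.1.3, 3.4.2.3), multiplying every baseline by 0.75 leaves the treatment estimate and p-value for the change unchanged, and the SPP may scale AUC anyway. A reader might convert the weaker covariate into a number of lost subjects. That needs within-day and baseline-to-outcome correlations that the documents do not give, and no power is claimed for the CGM endpoints.

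**Conclusion.** The concern holds as a contradiction about when the first sensor goes on, combined with a CGM baseline window that neither supplied document defines. If Protocol 3.1.1 and the synopsis are followed, about 18 h (72 of 96 readings) precede the first SC dose at matching clock times, and 16 to 22 h (64 to 88 readings) for a Day 1 shift of -2 to +4 h. Both the matching clock time and the range of shifts are assumptions.

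The consequences are limited to secondary endpoints. Descriptive within-arm changes are distorted: AUC over 24 h if it is not scaled to hours observed, and SD, CV and MAGE through the missing meal excursion. The baseline covariate is somewhat weakened, by an amount that cannot be estimated from the documents. The primary MMTT endpoint is unaffected. For an exploratory Phase 2a study this is a minor-to-moderate issue, worth correcting because the correction is cheap.

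**What to change.** **Protocol.** Reconcile the synopsis, 3.1.1 and footnote w: fit the first sensor on Day -1 before the meal test and at least 24 h before the planned Day 1 SC dose, with same-time predose changes on Days 14 and 28. Both conditions are needed. At equal clock times, a fitting just before the drink (T + 2 h) still gives only 22 h, while one at or before T gives the full 24 h.

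**SAP.** Define the CGM baseline as the 24 h before the first SC dose, and compare it with the same clock hours on Days 7, 14 and 28. Align the mention of Day -1 baseline readings in Protocol 4.3.6.1 with that definition. If the SPP already sets a window, state it in the SAP.

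**If the fitting time stays after the meal test.** Correct the footnote w example and compare the same available clock hours on all days.

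**Cost.** A small procedural amendment under Protocol 7.5, if judged substantial, plus SAP wording. Subjects are already inpatients from Day -2, so no visit or sensor is added, and Day -1 to Day 14 and Day 14 to Day 28 remain 14 days each. The downside is a few more hours of wear and a baseline day that contains the MMTT drink. That matches Day 28 but not the standardized breakfast on Days 7 and 14, so some difference in meal content remains at two of the three time points.
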